7.3. Long Term Follow-up: 6 and 12 & 24 months

Follow-up data collection will be conducted at approximately 6, 12, and at 24 months post-transplant.

7.3.1. 6 and 12-Month Follow-up

At approximately 6 and 12 months post-transplant, the patient will be evaluated at an office visit if this is the institution's standard of care, and, if not, by phone contact by the site. The patient's medical record may be reviewed to confirm patient's answers. This follow up will collect information on:

- Patient and graft survival;
- Liver graft related SAEs (6 months only);
- Liver graft related re-hospitalized after initial discharge, and, if yes, the primary reason/diagnosis for the hospitalization and the length of stay;
- Information will also be collected on any diagnosis of ischemic biliary complications and, if so, the method of diagnosis and treatment.

The 6 and 12-month follow-up will be collected within \pm 1 month of the designated period and will be recorded on the 6 and 12 month follow-up electronic form.

7.3.1.1. 24-Month Follow-up

At approximately 24 months post-transplant, the patient will be evaluated at an office visit if this is the institution's standard of care, and, if not, by phone contact by the site. The patient's medical record may be reviewed to confirm patient's answers. This follow up will collect information on:

- Patient and graft survival;
- Results of standard clinical practice or for cause liver biopsy will be collected (if applicable).

The 24 months follow-up will be collected within \pm 1 month of the designated period and will be recorded on the 24-month follow-up electronic form.

8. EVALUATION OF ADVERSE EVENTS

8.1. Evaluation of Liver Graft-Related Adverse Events

Liver Graft-Related Adverse Events are those, which have any untoward effect on the health, or safety of the patient and that are related to the transplanted Liver function (except for acute rejection). Liver graft-related adverse events will be collected from the time a subject is transplanted with a Liver preserved on OCS or Control until the completion of the 30-day follow-up evaluation. A Liver graft-related adverse event will be followed until resolution or stabilization of the event.

8.2. Serious Adverse Events (SAEs)

An adverse event will be classified as serious if it meets any of the following criteria:

- Results in, leads to, or contributes to, a death;
- Is life-threatening;
- Results in permanent disability or incapacity (i.e., permanent impairment of a body function or permanent damage to a body structure);
- Requires in-patient hospitalization or prolongs hospitalization;
- Necessitates medical or surgical intervention to preclude a permanent disability or incapacity;
- Results in fetal distress, fetal death or a congenital anomaly/birth defect

All Liver graft-related SAEs will be followed until their resolution.

8.3. Anticipated and Unanticipated Adverse Events

The investigator will assess each adverse event for whether it is anticipated or unanticipated. An unanticipated adverse event is defined as any adverse effect on health or safety, or any life-threatening problem or death caused by, or associated with, a device if that effect, problem or death was not previously identified in nature, severity or degree of incidence in the investigational plan or application (including a supplementary plan or application), or any other unanticipated serious problem associated with a device that relates to the safety, or welfare of subjects.

Adverse events are associated with Liver transplant procedures and have been documented within the first 30 days after Liver transplant, and are therefore anticipated. The list of events includes, but is not limited to:

- Acute rejection
- Atrial and ventricular arrhythmias
- Bleeding
- Hemodynamic instability
- Death
- Fever
- Early liver allograft dysfunction (EAD)
- Respiratory failure
- Liver primary non-function
- Bile leaks
- Hepatic artery thrombosis
- Portal vein thrombosis
- Cholangitis
- Liver abscess
- Diaphragmatic injury
- Phrenic nerve injury
- Sepsis
- Renal dysfunction and/or failure
- Hyperammonaemia

- Malignancy (post-transplant lymphoproliferative disorder (PTLD))
- Multiple organ failure
- Myocardial infarction
- Neurological dysfunction
- Hepatic dysfunction
- Diabetes due to steroid and anti-rejection medications
- Pancreatitis
- Peptic ulceration
- Gastritis
- Gastro esophageal reflux disease (GERD)
- Aspiration
- Cardiac tamponade
- Pneumo-mediastinum
- Pneumothorax
- Hemothorax
- Ascites
- Pleural effusion
- Venous thromboembolism (deep venous thrombosis [DVT])
- Pulmonary embolism (PE)
- Abdominal wound dehiscence
- Organ deemed not transplantable after retrieval
- Stroke
- Psychosis
- Ileus
- Bowel obstruction
- GI Bleeding (upper or lower)
- Cerebrovascular accident
- Peripheral vascular clotting or occlusion due insertion of mechanical support or equivalent
- Delirium, confusion and neurological complications
- Hepatic coma
- Retransplantation
- Limb gangrene due to vascular occlusion due insertion of mechanical support
- Use of mechanical circulatory support
- Coagulopathy
- Blood product transfusion
- Transfusion reaction
- Hyperacute rejection
- Anastomotic site complications; narrowing, bleeding or occlusion
- Bowel thromboembolic complications and gangrene
- Protamine and other anti-heparin medication reaction
- Heparin induced thrombocytopenia

8.4. Unanticipated Adverse Device Effect (UADE)

An UADE means any serious adverse effect on health or safety or any life-threatening problem or death caused by, or associated with, a device, if that effect, problem, or death was not previously identified or encountered before at least once in standard clinical practice, in nature, severity, or degree of incidence in the investigational plan or application (including a supplementary plan or application), or any other unanticipated serious problem associated with a device that relates to the rights, safety, or welfare of subjects.

8.5. Recording and Reporting of Adverse Event

All Liver graft-related adverse events and serious adverse events are to be recorded on the electronic case report forms until post-transplant day 30 or until initial hospital discharge, whichever comes first. The description of the adverse event will include: the date of onset, duration, severity, seriousness, the relationship of the event to the trial treatment, anticipated or not, and any treatment required. All serious adverse events occurring during the course of the first 30 days post-transplant will be reported to TransMedics, Inc., as well as documented on the appropriate electronic case report form(s). For all SAEs, the investigator is required to supply any additional data that may be deemed necessary by the Sponsor. Additionally any serious adverse events (SAE) and unanticipated adverse device effects (UADE) should be reported to TransMedics, Inc., preferably within 48 hours of the time the investigator learns of the event, but in no case later than 5 working days. Liver graft-related AEs will be recorded up to the 30-day follow-up or through hospital discharge only if longer than 30 days. For any particular patient, the Independent Medical Monitor if required to protect patient safety may specify a different follow-up period. The Sponsor is responsible for the classification and reporting of Liver graft-related adverse events to the appropriate regulatory authorities, and for the on-going safety evaluation of the trial in accordance with ISO 14155 and governing regulatory requirements.

8.6. Relationship of an Adverse Events to OCSTTM Liver (OCS) or Standard of Care (Control)

The investigator will assess the relationship of the AE to the OCS or Control methods of preservation. The relationship will be assessed using the following categories:

- **Definitely Related:** There is a reasonable causal and temporal relationship between preservation with the OCSTTM Liver and the adverse event.
- **Probably Related:** It is more likely than not that there is a reasonable causal relationship between preservation with the OCSTTM Liver and the adverse event.
- **Possibly Related:** There is a reasonable relationship with preservation with the OCSTTM Liver and the adverse event, but the causal relationship is unclear or lacking.
- **Unlikely Related:** There is a temporal relationship with preservation with the OCSTTM Liver and the adverse event, but there is not a reasonable causal relationship between the trial device and the event.
- **Unrelated:** There is no relationship between preservation with the OCSTTM Liver and the adverse event.

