7. TRANSPLANT, IMMEDIATE POST-OPERATIVE AND LONG TERM FOLLOW-UP

7.1. Transplant Details

The following information concerning the transplant procedure will be collected:

- The organ recipient unique post-transplant patient identifier
- Total cross clamp duration in minutes (from donor cross-clamp application to removal of cross-clamp in the recipient)
- Total cold ischemia time will be collected (Control= total cross clamp time; OCS = cold ischemic time pre and post OCS Liver perfusion)
- Any surgical complications encountered during surgery
- Use of circulatory bypass will be recorded
- Type of liver anastomosis
 - Bicaval anastomosis; or
 - Piggyback anastomosis
- The total amount of any blood product and clotting factors transfusion will be collected (pRBCs, Fresh Frozen Plasma (FFP), platelets, etc.)

- Any inotropic support needed to maintain hemodynamics will be collected for both arms
- A liver tissue biopsy will be collected from Right lobe of the transplanted liver immediately before abdominal closure in the recipient. The biopsy will be collected according to Liver Biopsy protocol in [Appendix 1](#).

7.2. Post-transplant Functional Assessments Day 0 – Day 30:

- **Early Liver Allograft Dysfunction (EAD) Surveillance in the first 7 days:**
 - AST level >2000 IU/ml within the first 7 postoperative days;
 - Bilirubin ≥ 10 mg/dl on postoperative day 7;
 - INR ≥ 1.6 on postoperative day 7; or
 - Primary non-functioning graft within 7 days
- **Inotropic Support to Maintain Hemodynamics at T0, T24 and 48 and 72 hours after ICU admission (if applicable) will be collected**
- **Initial use of Mechanical Respiratory Support:** duration of initial post-transplant invasive ventilator support will be recorded from the time of initial admission to ICU post-Liver transplant until extubation.
- **Initial Post-Transplant ICU Stay:** Intensive care unit (ICU) admission time, and date and time when clinical order for ICU discharge is written.
- **Renal Replacement Therapy:** Need for dialysis treatments in the first 10 days post liver transplantation for patients that did not have renal replacement prior to transplantation
- **Immunosuppression Medications:** The type of immunosuppression medication and dose will be recorded at day 7 and at time of discharge from the hospital. Immunosuppression induction will be recorded if applicable.

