- **Patient and Graft Survival at Day 30 and At Initial Hospital Discharge:** Patient and graft survival will be assessed on day 30 post-transplant and at initial hospital discharge post-liver transplantation.
- **Adverse Events:** All Liver graft-related serious adverse events and any Liver graft-related adverse events will be followed and documented until the investigator designates the event to be either resolved or its effect on the patient's condition stabilized.
- **Medications:** Medications used to treat all serious Liver graft-related adverse event (SAE)-related will be recorded in the trial electronic database until the SAE is resolved.

These follow-ups will be attempted within ± 3 days of the designated periods except for the Early Liver Allograft Dysfunction (EAD) Surveillance, in the first 7 days which must be collected at the designated times. The evaluations may be conducted over several days.

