APPENDIX 2. SCHEDULE OF CLINICAL ASSESSMENTS

Evaluations	Donor & Liver Assessments	
	OCS Preservation	Cold Flush and Storage (Control)
Eligibility & ID	X	X
Demographics/Characteristics	X	X
Donor Cause of Death	X	X
Donor Medical & Social History	X	X
Donor Liver Assessment	X	X
Donor Cross Clamp Time and Flush Detail	X	X
Post-Preservation Liver Biopsy and if applicable Bile duct specimen	X	X
OCS Preservation Parameters	X	
OCS Liver Enzymes & Lactate Levels	X	
Device Malfunction (if applicable)	X	
Non-transplant Reasons (if applicable)	X	X

Evaluations	Recipient Schedule of Assessments					
	Tx. Day -Day 7 Post-Tx.	Discharge	Day 30	Month 6	Month 12	Month 24
Eligibility & Informed Consent	X					
Randomization	X					
Demographic/Characteristics	X					
Medical & Risk Factors	X					
Transplant Details	X					
Early Liver Allograft Dysfunction (EAD) Surveillance	X					
Mechanical Ventilator Support	X					
Patient Survival	X	X	X	X	X	X
Graft Survival	X	X	X	X	X	X
Immunosuppressive Meds & Induction (if applicable)	X	X				
Initial ICU & Hospital Stay	X	X				
Liver Graft-Related (AE's & SAE's)	X	X	X			
Liver Biopsy *	X				X	X

* ONLY Tests regularly scheduled per center standard of care or performed due to a clinical cause at these time-points will be collected.

**APPENDIX 3. DRAFT PATIENT INFORMED CONSENT FORM
TEMPLATE**

(This Page is Intentionally Left Clear)

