4.4. Safety Endpoint

Safety will be analyzed principally by examination of the frequency of liver graft-related serious adverse events (SAEs) up to the 30-day follow-up after transplantation. This endpoint is defined as the number of liver-graft related serious adverse events through 30 days post-liver transplantation per subject, consisting of the following serious adverse events (at most one per type per person):

- Primary non-function (defined as irreversible graft dysfunction requiring emergency liver re-transplantation or death within the first 10 days, in the absence of immunologic or surgical causes)
- Ischemic biliary complications (ischemic biliary strictures and non-anastomotic bile duct leaks)
- Vascular complications (liver-graft related coagulopathy, hepatic artery stenosis, hepatic artery thrombosis, and portal vein thrombosis)
- Liver allograft infections (liver abscess, cholangitis, etc.)

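### The opening sentence of Protocol 8.5 lets adverse-event recording end at discharge, contradicting the rest of 8.5, Section 8.1, Appendix 2 and the 30-day safety endpoint

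*Protocol*

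**What the plan says.** Protocol Section 8.5 states a recording period three times.

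- The opening sentence has graft-related AEs and SAEs entered on the eCRF "until post-transplant day 30 or until initial hospital discharge, whichever comes first".
- The third sentence has no discharge cut-off. It says that all SAEs arising in "the first 30 days post-transplant will be reported to TransMedics, Inc., as well as documented on the appropriate electronic case report form(s".
- A later sentence reads: "Liver graft-related AEs will be recorded up to the 30-day follow-up or through hospital discharge only if longer than 30 days".

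Other parts of the plan bear on the same window:

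- Section 8.1 collects graft-related AEs from transplant "until the completion of the 30-day follow-up evaluation".
- Section 7.2, which covers Day 0 to Day 30, lists graft-related AEs and SAEs among its assessments.
- Appendix 2 marks the graft-related AE and SAE row at Discharge and again at Day 30.
- Protocol 4.4 and 9.4 set the principal safety endpoint over 30 days. SAP 4.4 agrees: "This endpoint is defined as the number of liver-graft related serious adverse events through 30 days post-liver transplantation per subject".

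For later follow-up, the synopsis and Section 7.3.1 collect graft-related SAEs at 6 months only. The 12-month contact collects patient and graft survival, ischemic biliary complications and graft-related re-hospitalisations. SAP Tables 3.1.5 and 3.1.6 are nevertheless titled as graft-related SAEs through 12 months.

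**The concern.** The three sentences of 8.5 cannot all be followed for a patient who leaves hospital before Day 30. The opening sentence stops recording at discharge; the other two do not. The only tie-breaker in 8.5 lets the Medical Monitor set a different follow-up period for a particular patient, which does not settle the general rule.

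The principal safety endpoint is a per-subject count of graft-related SAEs through Day 30. If a site took the opening sentence as its instruction, the observation window would end at discharge. It would then vary with length of stay, which is itself a post-randomization outcome listed under Other Endpoints. Non-serious graft-related AEs, which are tabulated but not part of the endpoint, are more exposed because fewer other provisions cover them.

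The two SAP tables raise a separate question of completeness. A reader would take their counts as full 12-month counts of graft-related SAEs, although that class is not collected after Month 6.

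**Working it through.** The plan states no figure to reproduce here. The check is a comparison of windows, plus simple arithmetic for scale.

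**1. Last day recorded under each rule.** Let D be the day of initial discharge, and take the 30-day follow-up as falling on Day 30.

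| Source | Rule | D = 12 | D = 14 | D = 34 | D = 88 |
|---|---|---|---|---|---|
| 8.5, opening sentence (graft-related AEs and SAEs) | min(30, D) | 12 | 14 | 30 | 30 |
| 8.5, SAE sentence (all SAEs) | 30 | 30 | 30 | 30 | 30 |
| 8.5, later sentence (graft-related AEs) | max(30, D) | 30 | 30 | 34 | 88 |
| 8.1 (graft-related AEs) | 30-day evaluation | 30 | 30 | 30 | 30 |
| Safety endpoint (graft-related SAEs) | 30 | 30 | 30 | 30 | 30 |

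For discharge before Day 30, the opening sentence alone falls short of the endpoint. For discharge after Day 30, the later sentence of 8.5 differs from the opening sentence and from 8.1, but only outside the endpoint window. Section 7.2 allows ±3 days around its follow-ups, so the 30-day evaluation may fall anywhere from Day 27 (30 − 3) to Day 33 (30 + 3). Day 30 and completion of the evaluation are therefore not the same end point.

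**2. How the analysis treats an unrecorded event.** SAP 13 compares mean counts by t-test, with no adjustment for time observed. SAP 5.3 imputes only the primary effectiveness endpoint and the two survival endpoints. An event that never reaches the database therefore counts as none. If both arms kept the same fraction r of their events, a true difference Δ would appear as r × Δ. That helps non-inferiority when OCS is worse (Δ > 0) and works against the superiority test when OCS is better (Δ < 0). Nothing in the documents establishes that r is equal in the two arms, so this direction is conditional.

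**3. Scale in time.** The only hospital stays in the documents are in Protocol 1.4.4, for another perfusion device: median 12 days (range 6–34) with machine perfusion and 14 days (range 8–88) with cold storage. Assume that stay is counted from transplant and that a site follows only the opening sentence. The unrecorded share of the 30-day window is then 1 − stay/30, with a floor of 0.

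- Medians: 1 − 12/30 = 60%; 1 − 14/30 = 53%.
- Shortest stays: 1 − 6/30 = 80%; 1 − 8/30 = 73%.
- Longest stays (34 and 88 days): 0%.

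**4. What would still catch an SAE.** The SAE sentence of 8.5 covers all SAEs to Day 30. Section 13.2 requires SAE notification within 5 working days and death notification within 48 hours, with no discharge limit. The Day 30 assessment and the 6-month collection of graft-related SAEs and re-hospitalisations follow, and under 8.2 in-patient hospitalisation makes an event serious. One gap remains: the SAP 14 counts of re-hospitalised subjects start at the 30-day visit, so a re-admission between discharge and Day 30 would not appear in them.

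**5. The two SAP tables.** The titles run to Month 12, while graft-related SAEs as a class are collected at Month 6 only. What the 12-month contact does collect may reveal some later SAEs, but not the whole class.

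**The case against.** The strongest reply is that the endpoint counts only SAEs, and 8.5 itself, two sentences after the disputed clause, puts every SAE of the first 30 days on the eCRF. Section 13.2 requires SAE notification without reference to discharge, and Section 14.3 has monitors check that SAEs are identified and reported in time. A site that dropped post-discharge SAEs would be breaching the same section. This stands in large part: it limits the risk to the endpoint and leaves non-serious graft-related AEs as the more exposed class. It does not remove the contradiction, because the opening sentence names SAEs explicitly and no order of precedence is given.

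It is also fair to object that the time shares say little about events. Primary non-function, one of the four endpoint components, is limited to the first 10 days, inside both median stays used above. That objection stands in full.

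A reader might think that deleting the discharge clause is enough. It is not. The sentence would then end at Day 30, which is not completion of the 30-day follow-up, and it would still disagree with the later 8.5 sentence for stays over 30 days.

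**Conclusion.** The opening sentence of 8.5 is inconsistent with the rest of 8.5, with 8.1, with Appendix 2 and with the 30-day safety endpoint, and should be corrected. The consequence is conditional: graft-related events between discharge and Day 30 may go unrecorded at a site that follows that sentence over the others. For SAEs, several other provisions limit this.

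A reader might infer that endpoint events were lost, that more than half of them would be missed, or that the safety comparison is tilted toward non-inferiority. The documents support none of these. They give no event rates by day, no stays for this trial and no evidence of how sites read the section. The 53% and 60% are shares of calendar time, borrowed from another device's series under the assumptions stated. An effect on the conclusion at the margin of 1.00 is not shown.

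The mismatch in SAP Tables 3.1.5 and 3.1.6 is real but separate. It would be wrong to infer that nothing relevant is collected at 12 months, since survival, ischemic biliary complications and graft-related re-hospitalisations all are. Counts of other graft-related SAEs after Month 6 may be incomplete.

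**What to change.** 1. In the opening sentence of 8.5, replace the end point with one recording window for graft-related AEs and SAEs that runs at least through completion of the 30-day follow-up, regardless of discharge. Because that visit may fall before Day 30, say also that the window does not close before Day 30.
2. State the same window in the later graft-related AE sentence of 8.5 and in 8.1, including what happens for stays over 30 days.
3. Before database lock, check for all subjects that graft-related SAEs between discharge and Day 30 were captured. Use the Day 30 and 6-month forms and the underlying re-hospitalisation records, not the SAP counts that start at the 30-day visit.
4. Retitle SAP Tables 3.1.5 and 3.1.6, or footnote them. The footnote should say that graft-related SAEs as a class are collected only to 6 months; that the 12-month contact collects patient and graft survival, ischemic biliary complications and graft-related re-hospitalisations; and that counts of other graft-related SAEs after Month 6 may therefore be incomplete.

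The cost is three reconciled statements in the protocol (two in 8.5, one in 8.1), one data check, and a title or footnote on two tables. The endpoint, its test and its margin do not change.

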4.3. Other Endpoints

- Length of initial post-transplant ICU stay
- Length of initial post-transplant hospital stay
- Evidence of ischemic biliary complications diagnosed at 6 and at 12 months post-transplant
- Extent of reperfusion syndrome as assessed based on the rate of decrease of lactate over the following time points:
 - During a hepatic phase immediately before reperfusion of the transplanted liver
 - 30-40 minutes after hepatic artery and portal vein reperfusion of the transplanted liver
 - 90-120 minutes after reperfusion of the transplanted liver
- Pathology sample score for liver tissue samples taken at the following time points (applies to both OCS and Control arms):
 - Donor liver pre-retrieval
 - Post-OCS and Control preservation at the end of back preparation and immediately before the start of re-implantation

- 90-120 minutes after reperfusion of the transplanted liver

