In addition, the numbers and percentages of subjects experiencing at least one treatment-emergent adverse event (TEAE) in the following categories will be tabulated by treatment group: liver graft-related TEAEs, treatment-related (definitely or probably-related) TEAEs, serious TEAEs, and serious liver graft-related TEAEs. The number of treatment-emergent liver graft-related adverse events, treatment-emergent serious adverse events (within 30 days post-

transplant and overall), treatment-emergent serious liver graft-related adverse events (within 30 days post-transplant and overall), treatment-emergent adverse events resulting in study discontinuation, and treatment-emergent serious adverse events with an outcome of death (within 30 days post-transplant and overall) will be tabulated by system organ class and preferred term using MedDRA (Version 13.0 or higher). Liver graft-related TEAEs and liver graft-related serious TEAEs will also be tabulated at the event level by system organ class and preferred term and the relationship of the liver graft-related adverse event to the investigational treatment using counts and percentages. Similar analyses at the event level will be performed by the severity of the adverse event.

The adverse event analyses above will also be presented by subgroup.

An exploratory analysis of the frequency of non-ischemic biliary complications through 30 days post-liver transplantation per subject will be performed. This endpoint will be summarized by treatment group using descriptive statistics. For each treatment group, a 95% confidence interval for the mean based on the t-distribution will be presented. Also, a 95% confidence interval based on the t-distribution will be presented for the difference in means between the two treatments.

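### The protocol gives three different recording windows for liver graft-related AEs, two of them dependent on hospital stay, and the SAP tabulates these AEs by arm with no day-30 cut-off

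*Protocol*

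**What the plan says.** **Recording.** The protocol states the end of AE recording in three ways.

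- Section 8.1: graft-related AEs are collected from transplant "until the completion of the 30-day follow-up evaluation".
- Section 8.5, first sentence: graft-related AEs and serious AEs "are to be recorded on the electronic case report forms until post-transplant day 30 or until initial hospital discharge, whichever comes first".
- Section 8.5, later: "Liver graft-related AEs will be recorded up to the 30-day follow-up or through hospital discharge only if longer than 30 days".

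Section 8.5 adds that for a particular patient "the Independent Medical Monitor if required to protect patient safety may specify a different follow-up period". It also separately requires all serious AEs in the first 30 days to be reported and entered on the eCRF. Section 7.3.1 collects graft-related SAEs again at 6 months for all recipients.

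**Analysis.** SAP 13 tabulates by treatment group the subjects with at least one event in these classes: "liver graft-related TEAEs, treatment-related (definitely or probably-related) TEAEs, serious TEAEs, and serious liver graft-related TEAEs". The tabulation by system organ class and preferred term begins "The number of treatment-emergent liver graft-related adverse events, treatment-emergent serious adverse events (within 30 days post"; the 30-day qualifier belongs to the second item, not to the first. In the SAP's List of Tables, serious graft-related events have 30-day tables (3.1.3, 3.3.3.2) beside an overall table (3.3.3.1). Tables 3.3.1.1, 3.3.2.1, 3.3.6.1 and 3.3.7.1 have no time limit in their titles and no 30-day counterpart. The SAP text defines no treatment-emergent window. "Length of initial post-transplant hospital stay" is itself listed among the other endpoints (SAP 4.3, protocol 4.3).

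**The concern.** An AE count is comparable between arms only if both arms are observed for the same time, or if the time is accounted for. Two of the three rules make observation time a function of length of stay, which preservation method may change. If OCS shortened stays, Control would be observed longer; if OCS lengthened them, the reverse. Under the later-of rule the extra time falls on recipients still in hospital after day 30, who are likely to be the most complicated cases. Under the earlier-of rule the lost time falls on recipients discharged before day 30.

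The four tables take whatever was recorded. Their by-arm counts and percentages, including those by relationship and severity, could therefore mix risk with length of observation. They also combine non-serious AEs, which have no later collection, with SAEs that are collected again at 6 months.

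**Working it through.** **1. The three rules side by side.** Let L be the initial stay in days and W the recording window.

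| Rule | Source | W | L = 12 | L = 45 |
|---|---|---|---|---|
| Fixed | 8.1 | 30 | 30 | 30 |
| Earlier-of | 8.5, first sentence | min(30, L) | 12 | 30 |
| Later-of | 8.5, later sentence | max(30, L) | 30 | 45 |

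Both min(30, L) and max(30, L) rise or stay level as L rises. So under either one, an arm with a distribution of stays shifted upward has a mean window at least as long. Only the fixed rule removes the dependence.

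**2. Does the SAP close the gap?** For the principal safety endpoint, yes: it counts events through day 30. For serious graft-related events a 30-day table exists. For all graft-related TEAEs, neither SAP 13 nor the table titles give a cut-off.

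**3. Size, as an illustration only.** The documents give no figure for this trial. The feasibility table in protocol 1.4.4 reports hospital stay as median 12 (range 6-34) days with machine perfusion, n = 20, and 14 (8-88) with cold storage. The cold-storage n is inferred: 9 events are given as 22.5%, and 9/0.225 = 40. Stays are assumed lognormal with median m and log-SD s. With d = (ln m − ln 30)/s:

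- P(L > 30) = Φ(d)
- added time a = E[max(L − 30, 0)] = m·exp(s²/2)·Φ(d + s) − 30·Φ(d)
- mean window = 30 + a (later-of), or m·exp(s²/2) − a (earlier-of)

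The spread is not reported, so s was set in five ways. The expected largest of n standard normal values is 1.867 for n = 20 and 2.161 for n = 40.

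- Full range: ln(34/6)/(2 × 1.867) = 0.464; ln(88/8)/(2 × 2.161) = 0.555.
- Maximum only, by expected maximum: ln(34/12)/1.867 = 0.558; ln(88/14)/2.161 = 0.851.
- Maximum only, placed at the n/(n+1) quantile: 0.624 and 0.933.
- Common s of 0.6 or 0.8 in both arms.

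Results under the later-of rule, machine perfusion against cold storage:

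| Spread | P(L > 30) | Mean window, days | Gap, days | Ratio |
|---|---|---|---|---|
| Common 0.6 | 6.3% vs 10.2% | 30.64 vs 31.15 | 0.5 | 1.02 |
| Full range | 2.4% vs 8.5% | 30.15 vs 30.83 | 0.7 | 1.02 |
| Common 0.8 | 12.6% vs 17.0% | 32.25 vs 33.36 | 1.1 | 1.03 |
| Expected maximum | 5.0% vs 18.5% | 30.44 vs 34.14 | 3.7 | 1.12 |
| Maximum at quantile | 7.1% vs 20.7% | 30.78 vs 35.61 | 4.8 | 1.16 |

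Under the earlier-of rule the same five settings give mean windows of 13.2 to 14.3 against 15.5 to 16.0 days, a gap of about 1.6 to 2.4 days. Under the fixed rule, or with equal stay distributions, the gap is zero.

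The two fits to the maximum alone deserve least weight. With s = 0.851 the implied smallest of 40 cold-storage stays, on the log scale, is 14·exp(−0.851 × 2.161) = 2.2 days, where the table reports 8. One 88-day stay drives those rows.

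**The case against.** The strongest case on the other side has four parts.

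- *Section 8.1 already gives a fixed window.* If it governs, there is no stay-dependence. That is true, but nothing in the protocol says that 8.1 overrides 8.5. A reader might infer from the later sentence of 8.5 alone that recording definitely runs to discharge in long stays. The documents do not support this either, because the first sentence of 8.5 says the opposite.
- *Little is exposed.* The principal safety endpoint stops at day 30, serious graft-related events have 30-day tables, and graft-related SAEs are collected again at 6 months. SAP 13 describes the four tables as counts and percentages and names no test for them; SAP 5.9 excludes testing in the AE subgroup tables. This stands. It confines the point mainly to non-serious AEs in descriptive tables.
- *The figures are borrowed.* They come from another perfusion device, with an inferred n and an assumed distribution. This stands. They show a range, not an expected bias in this trial.
- *A day-30 filter on every graft-related table would discard valid data.* This also stands. The planned overall serious tables include events collected at 6 months whatever the stay, so those tables should remain. Nor can a filter restore events that were never recorded under the earlier-of rule.

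**Conclusion.** The point holds as an inconsistency in the recording rules combined with a missing cut-off in four descriptive tables. It is minor and cheap to correct. Under the later-of rule the illustrative gap in mean window is about 0.5 to 5 days, or 2% to 16%; the fit that uses the whole reported range gives 0.7 days, about 2%. The gap is zero if stays are alike. A percentage of window length is not a percentage of events, because the documents give no AE rate after day 30.

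Two stronger readings are tempting. One is that the comparison is biased against a particular arm. The documents do not support this: the direction depends on which arm stays longer in this trial, which is unknown, and on which recording rule was applied. The other is that the principal safety endpoint is compromised. Under the later-of rule it is not affected. Under the earlier-of rule its completeness after discharge relies on the separate requirement in 8.5 to report all SAEs in the first 30 days, so it is protected as long as that requirement is followed.

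**What to change.** 1. **Protocol 8.1 and 8.5:** reconcile the three statements so that all recipients share one recording window covering at least days 0-30, whatever their discharge date. State how any period set by the Medical Monitor for an individual patient is handled in the tables.
2. **SAP 13:** add versions of Tables 3.3.1.1, 3.3.2.1, 3.3.6.1 and 3.3.7.1 restricted to onset on days 0-30, and name these as the versions for the between-arm reading.
3. **Keep** the overall serious graft-related tables. List non-serious graft-related events with onset after day 30 separately by arm.
4. If recording stopped at discharge for any recipient discharged before day 30, report how many by arm, since the date filter cannot recover those events.

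Cost: a clarification of the protocol text, four further tables and a listing. Onset date is already collected under 8.5, so the tables need only a date filter. No planned table is lost.
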